4.1.4 Target Accrual and Study Duration

Eight patients in the Phase I (Cohort 0), and 18 patients will be enrolled in the Phase II Cohort A (8 already enrolled under Phase 1 portion of Cohort A from previous protocol version) and 39 in Cohort B (65 patients total). It is expected to have up to 32 patients enrolled from accompanying external sites and the remainder enrolled from Roswell Park. Accrual is expected to take up to 10 years.

Patients will be drawn from the interventional pulmonology practice and from referrals from medical oncologists. All patients will come off study at 24 weeks.

Enrolled patients who do not receive the I-PDT and/or PDT for any reason (such as patient withdrawal, safety or inability to deliver the I-PDT) will be replaced.

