8.1.9 Long Term Follow-Up Evaluations

The following evaluations will be performed at 8 weeks (± 2 weeks), 12 weeks (± 2 weeks) and 24 weeks (± 4 weeks) after last study I-PDT and/or PDT (or when clinically indicated):

Physical examination (including vital signs)

ECOG Performance Status (Appendix A)

Concomitant medications: Required as indicated throughout the long-term follow-up period so that any medications that may interfere with immune function are documented.

Chest CT scan

Quality of Life Questionnaire at 12 and 24 weeks (Cohorts A and B; Appendix D)

Six-Minute Walk Test at 12 weeks and 24 weeks (Cohorts A and B)

8.1.10 Patients coming off the study:

• Patients will be taken off the study and no data will be collected after the follow-up visit at 24 weeks (± 4 weeks) after the last I-PDT and/or PDT.

• All patients, including those that progress prior to 24 weeks, will continue to be followed for disease and survival status for the full 24 weeks.

Progression of disease will not cause the patients to be off study. We will continue to collect response data as it will be part of standard of care for these patients. We will use modified RECIST 1.1 to determine response.

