8.1.11 Schedule of Procedures and Observations

The schedule of procedures and observations for this study is summarized in Table 1 below.

Evaluation	Baseline ¹	Day -3	Day -2	Day -1	Scheduled EBUS I- PDT (Day 0)	Days 1 through 3	Days 2 through 10 ²²	7-10 Days Post- Procedure	Initial Follow-Up ² Evaluation	Long Term Follow-Up ³ Evaluation s
Medical History	Х									
Pre-Existing Conditions	Х									
Physical Examination, including vital signs ⁴	Х				X ⁵		X ^{5,22b}		X	Х
Hematology ⁶	Х		X ²⁴		X ²⁴				X	
Blood Chemistry/creatinine clearance ⁷	Х		X ²⁴		X ²⁴				X	
Pregnancy Test (Urine/Serum)	X^8									
ECOG Performance Status (Appendix A)	Х								X	Х
Tumor/Disease Assessment: Contrast Enhanced CT scan (chest) ⁹ (non-contrast CT if the patient has allergy to the contrast agent)	X9								X9	X9
Injection of porfimer sodium			X							
Diet prior to I-PDT procedure					X ²⁰		X ^{20a}			
Cohort B Only: SOC palliative radiotherapy			X ²²							
SOC Bronchoscopy/EBUS- TBNA					X ¹⁰				X ¹¹	
EBUS color Doppler to identify vasculature					Х					
Tumor Debulking, Ablation and/or Airway Stenting					Х		X			

Table 1Schedule of Procedures and Observations

Evaluation	Baseline ¹	Day -3	Day -2	Day -1	Scheduled EBUS I- PDT (Day 0)	Days 1 through 3	Days 2 through 10 ²²	7-10 Days Post- Procedure	Initial Follow-Up ² Evaluation	Long Term Follow-Up ³ Evaluation s
If possible, optical and pO2 measurements immediately before and after I-PDT					X ²³					
I-PDT ¹² guided with EBUS- TBN and/or I-PDT and/or PDT					X					
Immune marker blood and tumor tissue sampling ¹³			X		Х			Х	Х	
Pre-I-PDT and/or PDT tissue sample					X ^{14,14a}		X ^{14b}		X ¹⁴	
Concomitant Medications	X ¹⁵				Х		X ^{22b}		Х	X ¹⁶
Adverse Events					X		X ^{22b}		Х	
Quality of Life Questionnaire (Appendix D) ¹⁷	Х								Х	X ¹⁸
Six-Minute Walk Test ²¹	Х									X ¹⁸
Survival Status										X ¹⁹

1 Performed within 4 weeks prior to scheduled EBUS I-PDT, as part of standard of care for the therapeutic bronchoscopy, unless otherwise indicated.

2 Initial Follow-Up evaluation at 4 ± 1 weeks after the last I-PDT and/or PDT treatment (dependent on severity of disease and clinical condition of patient).

3 Long-Term Follow-Up routine will be performed only when clinically indicated, at these visits: 8 weeks (± 2 weeks), 12 weeks (± 2 weeks), and 24 weeks (± 4 weeks) after the last I-PDT and/or PDT.

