4 Vital signs: temperature, heart rate, respiratory rate, blood pressure, body weight, and height. *Height collected at baseline only*.

5 To be performed prior to procedures as SOC and at post-operative evaluation after undergoing treatment. Note: on the day of scheduled bronchoscopy, weight is not needed at the preoperative and post-operative physical exam. Oxygen saturation to be measured pre- and post-operatively.

6 Standard of care - will be performed if indicated by the anesthesia pre-op assessment: Complete blood count (CBC) with automated differentials: WBC, RBC, HGB, HCT, platelet, MCV, MCH, MCHC, % neutrophils, absolute neutrophils, % monocytes, absolute monocytes, % eosinophils, absolute eosinophils, absolute basophils, % lymphocyte, absolute lymphocyte, platelet confirmation (as clinically indicated), and differential confirmation (as clinically indicated).

7 Standard of care - will be performed if indicated by the anesthesia pre-op assessment: Complete metabolic panel (CMP): chloride, CO₂, potassium, sodium, BUN, glucose, calcium, creatinine, total protein, albumin, total bilirubin, alkaline phosphatase, AST, ALT, A/G ratio, BUN/creatinine ratio, osmol (Calc), anion gap.

8 Within 7 days prior to study treatment. Serum HCG will be obtained if urine is not available.

- 9 CT scan will be within 2 weeks ± 1 week prior to study treatment. CT scan in Follow-Up, will be performed only when clinically indicated, at these visits: 4 weeks (±1 week), 8 weeks (±2 weeks), 12 weeks (±2 weeks), and 24 weeks (±4 weeks) after the last I-PDT and/or PDT.
- 10 Bronchoscopy (SOC) with EBUS-TBNA. The details of the interventional bronchoscopy procedure described in Section 6.1.2 are standard of care and, do not need to be documented in the Case Report form.
- 11 Schedule date/time for initial follow-up SOC bronchoscopy **without** EBUS-TBNA: TBNA will be performed only if clinically indicated outside the scope of this study. *Note*: Initial follow-up bronchoscopy will be performed within 4 weeks following the initial follow-up visit.
- 12 I-PDT and/or PDT will be performed with 630-nm light delivered through a cylindrical diffuser that will be inserted into tumor through a TBN with EBUS guided imaging. Endobronchial tumors can be treated with I-PDT and/or PDT. An endoscope will be used to guide the fiber placement.
- 13 Refer to Section 8.12
- 14 Refer to Section 8.13 for standard of care Pathology procedures.

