14a. Tissue is taken **before and after** I-PDT during the EBUS I-PDT. For the Tissue Immune Markers and Drug Uptake processing, tissue is taken **prior** to EBUS I-PDT, see Section 8.4. For the Tissue Sample for the STAT3 Crosslinking processing, tumor tissue is collected from the treated area immediately (within minutes) after EBUS I-PDT procedures, see Section 8.3

- 15 Required as indicated throughout the long-term follow-up period so that any medications that may interfere with immune function are documented.
- 16 List any ongoing medications with an onset within 1 week of study treatment.
- 17 Survey data will be stored in REDCap. Quality of Life Questionnaires do not apply to Cohort 0 participants.
- 18 Only required at 12 and 24 weeks.
- 19 For all patients, (including those with disease progression prior to 24 weeks), survival status will continue to be collected until 24 weeks. After 24 weeks they will come off study.
- 20 For day of EBUS I-PDT bronchoscopy (Day 0), starting at midnight, all participants are fasting at home per normal preparation procedures. Participants can eat after the procedure (according to the standard clinical instructions).
- 21 The Six Minute Walk Test does not apply to Cohort 0 participants.
- 22 Palliative radiotherapy of 8 Gyx1 will be administered to the target tumor at day -2 just before systemic administration of 2 mg/kg porfimer sodium. This will be coordinated with the radiation oncologist. This only applies to participants in Cohort B.
- 23 Optical measurements and tumor pO2 will be conducted as described in section 1.1.13, optional. The data will be saved on password secured computer in [name] laboratory. The CRF will only document that these measurements were done.
- 24 All participants will have a blood draw for CBC and CMP within 2 days prior to administration of porfimer sodium. Additionally, patients on chemotherapy will have a blood draw for CBC and CMP within 2 days prior to PDT.

If there are multiple PDT treatments for patients on chemotherapy, CBC and CMP will be done within 2 days prior to each treatment.

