9.2 Target Lesions

All measurable lesions up to a maximum of 2 lesions per organ and 5 lesions in total, representative of all involved organs, will be identified as target lesions and recorded and measured at baseline. Target lesions will be selected on the basis of their size. Lesions with the longest diameter (short axis for lymph nodes) and are $\geq 10 \text{ mm}$ (CT and MRI), $\geq 15 \text{ mm}$ lymph nodes, > 20 mm CXR and are for accurate repetitive measurements (either by imaging techniques or clinically) will be chosen. A sum of the longest diameter (short axis for lymph nodes) of all target lesions will be

calculated and reported as the baseline sum diameters. This will be used as reference to further characterize the objective tumor response of the measurable dimension of the disease.

The above standard RECIST technique will be used for measurement of the longest diameter of the target lesion.

NOTE: We will use I-PDT and PDT to treat *extrabronchial and endobronchial tumors*. The *extrabronchial* will be treated with EBUS-TBN I-PDT. *The endobronchial tumors (inside the airway) can be treated with* I-PDT and/or PDT. All treated tumors will be measured by CT scans (baseline and follow-up).

Tumors that are *inside* the airway that will be treated with laser, rigid bronchoscopy or ablation (see Section 6), *will not be measured on CT scan*.

Therefore, the volume of the tumor that will be treated with either EBUS-TBN I-PDT or with I-PDT and/or PDT will be measured on CT that was performed within 2 weeks ± 1 week before the procedure (refer to Section 8.1: Baseline Evaluations) will be compared to the volume of the I-PDT and PDT treated tumor on CT that is taken at initial follow-up bronchoscopy (refer to Section 8.1.5).

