9.2.1 Evaluation of Target Lesions

Tumor response assessments will be performed at 4 weeks (\pm 1week) following I-PDT and/or PDT (refer to Section 8.1.8).

- Complete Response (CR): Disappearance of all target lesions.
- **Partial Response (PR):** At least a 30% decrease in the sum of diameters of target lesions, taking as reference the baseline sum diameters.
- **Progressive Disease (PD):** At least a 20% increase in the sum of diameters of target lesions, taking as references the smallest sum on study (this includes the baseline sum if that is the smallest on study). In addition to the relative increase of 20%, the sum must also demonstrate an absolute increase of at least 5 mm.
- Stable Disease (SD): Neither a sufficient shrinkage to qualify for PR nor sufficient increase to qualify for PD, taking as reference the smallest sum diameter while on study.

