12.1.3 Primary Phase II Efficacy Analysis

The primary endpoint for Cohort A and Cohort B is the proportion of complete responders (CR) and partial responders (PR) as measured by RECIST v1.1 at 12 ± 1 week after DOSIETM (Cohort A) and COMSOLTM guided I-PDT.

For Cohort A, we hypothesize that the objective tumor response for CR+PR will be at least 29%. We also want to investigate the impact of variation in optical properties, Photofrin® retention, and fiber location perturbation on the objective tumor response. The primary analysis will consist of a one-sided exact binomial test of H₀: π =0.05 versus H_a: π >0.05 at level α =0.05, where π is the proportion of CR+PR responders. For Cohort B, the primary analysis will consist of a one-sided exact binomial test of H₀: π =0.30 versus H_a: π >0.30 at level α =0.05.

Additional clinical efficacy endpoints are: (1) changes from baseline to 3 months in the FACT-L Total Score related subscales (physical well-being, social/family well-being, emotional well-being, functional well-being); (2) the 6-minute walk measures (distance, VO2max, shortness of breath scores). All key clinical efficacy outcomes will be considered suitably continuous will be analyzed with an analysis-of-covariance (ANCOVA) approach regressing change from baseline to three months on the baseline value of the respective measure adjusted for baseline tumor volume, age, and sex.

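### The primary CR+PR test is set at 12 ± 1 week, but the response section names only week 4, the 12-week CT is conditional, and no rule covers death or a missing scan

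*Combined protocol and SAP*

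**What the plan says.** **Time point.** Section 12.1.3 defines the primary endpoint of Cohorts A and B as the proportion with CR or PR "as measured by RECIST v1.1 at 12 ± 1 week" after guided I-PDT. Section 9.2.1, which defines CR, PR, SD and PD, states "Tumor response assessments will be performed at 4 weeks", with a window of ± 1 week, and names no other time. Section 9.2 likewise compares baseline tumor volume with the "CT that is taken at initial follow-up bronchoscopy".

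**Whether the scan is done.** Section 8.1.9 lists a chest CT among evaluations at 8 weeks, "12 weeks (± 2 weeks) and 24 weeks (± 4 weeks) after last study I-PDT and/or PDT (or when clinically indicated"). Footnote 3 to Table 1 (Section 8.1.11) is firmer: "Long-Term Follow-Up routine will be performed only when clinically indicated". So is footnote 9: "CT scan in Follow-Up, will be performed only when clinically indicated, at these visits", and the visits it lists are weeks 4, 8, 12 and 24.

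**FACT-L and 6-minute walk.** Sections 4.1.2 and 12 also list these as primary endpoints. Footnote 18 on those rows reads "Only required at 12 and 24 weeks", whereas footnote 3 makes the visits conditional.

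**Window.** The 12-week visit and CT are allowed ± 2 weeks; the endpoint allows ± 1 week.

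**Denominator.** Section 4.1.4 replaces "Enrolled patients who do not receive the I-PDT and/or PDT for any reason" and goes no further. Section 12.1.8 defines who is evaluable for toxicity. Sections 9.2.4 and 12.1.4 count death as an event for PFS. I found no statement of how a treated patient who dies, or who has no 12-week scan, enters the CR+PR test.

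**The concern.** Someone following Section 9 would read the week-4 scan, and someone following Section 12 the week-12 scan. A site following the Table 1 footnotes may have no week-12 scan at all, and a site that scans within the visit window may still miss the endpoint window.

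Whether a patient is scanned can depend on how that patient is doing. If patients who decline go unscanned and are excluded, the response rate is biased up. If patients who do well go unscanned and are excluded, it is biased down. The documents give neither the share missing nor the mechanism, so the direction is unknown. With no efficacy analysis set stated, the denominator could be settled after the data are seen. Early deaths are foreseeable: Section 2 describes frail patients at a terminal stage, and Section 5.1 admits ECOG status up to 3.

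**Working it through.** **Inputs.** From Sections 12.1.3 and 12.1.6: one-sided exact binomial tests at α = 0.05. Cohort A has n = 18, null rate 0.05 and alternative 0.29. Cohort B has n = 39, null rate 0.30 and alternative 0.50. Power is set at 0.80 for both. The unscanned share is not given; 10%, 20% and 30% are assumed.

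**1. The plan's own figures.** The critical value r is the smallest integer with P(X ≥ r | n, p0) ≤ 0.05.

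| | r | Actual α | Power |
|---|---|---|---|
| Cohort A, n = 18 | 4 | 0.0109 | 0.812 at 0.29 |
| Cohort B, n = 39 | 17 | 0.04998 | 0.832 at 0.50 |

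The sample sizes hold, on the premise that every patient has a response result.

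**2. Can the choice of denominator change the verdict?** The p-value is P(X ≥ x | n, p0).

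- Cohort A, 3 responders: 3/18 gives 0.058 (fails); 3/16 gives 0.043 (passes).
- Cohort B, 16 responders: 16/39 gives 0.094 (fails); 16/36 gives 0.047 (passes).

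Excluding two or three patients is enough.

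**3. Worst case for false positives.** The true rate equals the null, all unscanned patients are non-responders, and they are excluded. With unscanned share m, three models:

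- (i) Scanned n fixed at k = n(1 − m), rounded; rate among the scanned p0/(1 − m); type I error P(Bin(k, p0/(1 − m)) ≥ r_k), where r_k is the critical value for k patients.
- (ii) Exactly n − k non-responders removed; type I error P(Bin(n, p0) ≥ r_k).
- (iii) Each non-responder unscanned with probability m/(1 − p0); critical value set by the number actually scanned.

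| Cohort B | k, r_k | (i) | (ii) | (iii) |
|---|---|---|---|---|
| 10% | 35, 16 | 0.087 | 0.094 | 0.088 |
| 20% | 31, 15 | 0.143 | 0.164 | 0.182 |

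| Cohort A | k, r_k | (i) | (ii) | (iii) |
|---|---|---|---|---|
| 10% | 16, 3 | 0.056 | 0.058 | 0.033 |
| 20% | 14, 3 | 0.053 | 0.058 | 0.051 |
| 30% | 13, 3 | 0.061 | 0.058 | 0.057 |

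Cohort A starts from an actual α of 0.011, so it ends at or barely above 0.05.

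**4. Opposite case.** Four Cohort B responders are unscanned and excluded. Then n = 35 and r = 16, so success needs 16 + 4 = 20 responders among the 39. P(Bin(39, 0.50) ≥ 20) = 0.500, against 0.832 with full data.

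**5. Neutral case.** Scans are missing independently of response and those patients are excluded. Cohort B type I error is 0.037 at 10% and 0.035 at 20%, so there is no inflation. With scanned n fixed at 35 and 31, power at 0.50 is 0.75 and 0.64.

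**6. Window.** The visit spans weeks 10 to 14 and the endpoint weeks 11 to 13. So 2 of the 4 permitted weeks lie outside the endpoint window. This is calendar time, not the share of scans affected.

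**The case against.** - **The scan is scheduled.** Section 8.1.9 lists a 12-week chest CT as an evaluation to be done, and its closing parenthesis can be read as allowing extra timing rather than omission. Section 8.1.10 keeps following patients after progression. This stands as a reading of Section 8.1.9, but footnotes 3 and 9 say the opposite, and Section 8.1.10 relies on response data arising from routine care without requiring a 12-week scan. Sites have two conflicting instructions.
- **The denominator is implied.** Replacing only untreated patients, with tests sized at 18 and 39, points to all treated patients. That is a fair inference, but those are planned sizes. No efficacy set is stated, and the inference does not classify an unscanned patient.
- **RECIST 1.1 may supply a rule.** That source is not part of the documents, so this cannot be checked here. If the sponsor relies on it, Section 12.1.3 should state the rule.
- **The FACT-L and walk conflict is weak.** Footnote 18 is the more specific note, and Section 8.1.9 names weeks 12 and 24 for both. This largely stands: it is a wording repair and does not touch the CR+PR test.
- **The type I figures are extremes.** True. The neutral case shows no inflation, and excluding only one or two non-responders from Cohort B leaves the error at 0.050. They bound what the open rule permits; they do not forecast it.
- **Other repairs would also work,** such as narrowing the visit window. True; what is essential is one time point, one window and one rule.

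**Conclusion.** The concern holds and should be fixed before analysis. The time, collection and denominator of the primary test are not settled. Following the plan as written, the primary scan can be skipped, or taken on schedule and still fall outside the endpoint window. Two or three exclusions can turn a failed test into a positive one in either cohort.

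The exposure is mainly in Cohort B, where α is already fully used at 0.04998: roughly 0.09 to 0.18 under the worst-case assumption at 10% to 20% unscanned, or power of 0.50 if four responders are lost. Cohort A's error stays near 0.05, but its verdict can still flip. All missing-data shares and mechanisms are assumptions. The conflicts between sections do not depend on them.

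**What to change.** 1. In Section 9.2.1, name 12 weeks as the primary response time, to match Section 12.1.3, and label the 4-week reading secondary. Align the volume comparison in Section 9.2.
2. In Section 12.1.3, use the ± 2-week visit window for the endpoint.
3. Make the 12-week CT, FACT-L and 6-minute walk scheduled study assessments by removing the clinical-need condition for them in footnotes 3 and 9 and in Section 8.1.9. If the 4-week reading is kept as secondary, remove the condition for the 4-week CT in footnote 9 too.
4. In Section 12.1.3, state that every treated patient is in the denominator and that death or no evaluable 12-week scan counts as non-response. Report a scanned-only analysis as a sensitivity analysis.

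**Cost.** Mostly wording, plus a fixed 12-week CT that Section 12.1.3 already needs and Section 8.1.9 already lists. Counting missing scans as non-response lowers the estimated rate and the power. If scans are missing independently of response, the rate counted as response is p1(1 − m), where p1 is the alternative rate:

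| Missing | Cohort B rate, power | Cohort A rate, power |
|---|---|---|
| 0% | 0.50, 0.83 | 0.29, 0.81 |
| 10% | 0.45, 0.63 | 0.261, 0.73 |
| 20% | 0.40, 0.38 | 0.232, 0.63 |

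That loss is the reason to require the scan as well as state the rule. For the 8 Cohort A patients enrolled under the previous protocol version (Section 4.1.4), a 12-week scan may not be retrievable. The sponsor should establish how many are affected before the rule is applied.

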1.1.10 EBUS Guided I-PDT Preceded by Standard of Care Palliative Radiotherapy

Following the completion of Cohort 0, we have recently reported that Photofrin® mediated interstitial photodynamic therapy (I-PDT), delivered via our image-guided light dosimetry planning platform, is safe with promising outcomes in the treatment of extrabronchial MCAO with 3 out of 10 patients alive at 8.3, 12, and 26.5 months (56). This study included patients with stage IIb-IVb of either non-small cell lung cancer, large cell neuroendocrine, melanoma, or endometrial cancer that metastasize to the airway causing extrabronchial MCAO. The Photofrin® was retained in all these tumors and responses did not seem to be affected by the cancer pathology. Our computer modelling suggests that we delivered the maximum safe light dose rate (irradiance) and dose (fluence). Careful analysis of the clinical outcomes indicates that further improvement in tumor control requires augmenting I-PDT with additional therapy.

We propose to improve the response to I-PDT with palliative radiotherapy (p-XRT). P-XRT is standard of care treatment for patients with refractory lung cancer (57, 58), and several groups have reported that it can increase tumor oxygenation and alter tumor vasculature for 1-2 days after the last radiation fraction (59-63). Our group and others have reported that increases in tumor hemoglobin oxygen saturation and vascular perfusion will increase tumor oxygenation and

penetration of the Photrofrin®-exciting 630-nm illumination laser light (64-68). This is accompanied by improvement in tumor response to PDT.

Preliminary preclinical data demonstrate that p-XRT followed by I-PDT provide for constructive cooperation between the modalities. In studies investigating this approach, we evaluated the preclinical response of two murine models to a regimen of p-XRT followed in 24 h by I-PDT (Figure 5). To demonstrate that p-XRT improves tumor response, we used low dose I-PDT in mice with locally advanced murine tumors (400-600 mm³). An X-radiation dose of 10 Gyx2 on consecutive days induced slight tumor growth delay, establishing it as a palliative regimen (palliative X-Radiation, p-XRT). As a standalone modality, the low dose I-PDT produced minimal to modest tumor control as a function of tumor model, as expected. When p-XRT is followed by I-PDT, there is significant (p<0.05) improvement in durable complete response in both models (Figure 5). This

p-XRT

_2000

I-PDT

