4.1.2 Primary Phase II Endpoints (Cohort A and Cohort B)

- Objective tumor response (CR, PR, PD, and SD)
- The FACT-L Total Score related subscale
- 6-minute walk measures.

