- Quality of Life Questionnaire (Cohorts A and, B): Quality of life will be assessed using the Functional Assessment of Cancer Therapy-Lung (FACT-L) scale. The 36 self-report items on the FACT-L measure six domains of quality of life (physical wellbeing, social/family well-being, relationship with doctor, emotional well-being, functional well-being, and additional concerns). FACT-L is written at a sixth grade reading level and takes an average of 7 minutes to complete. It is based upon recall over the last seven days of time. FACT-L was chosen because multiple studies support its validity and use in clinical trials of lung cancer (73, 74, 88, 89). It has been used across Phase 1-Phase 3 clinical trials. Additionally, prior research has quantified the minimal clinically important difference, and has been used to distinguish complete responders from non-responders in other studies (54). Study subjects will be given the questionnaire (see Appendix D) at time of study enrollment and at each follow up visit until study completion via tablet (or paper questionnaire if tablets are unavailable at that time).

- Six-Minute Walk Test (Cohorts A and B): The Six-Minute Walk Test is the most used measure of functional capacity in lung cancer (55, 70). As the pathophysiology of central airflow obstruction is similar regardless of the underlying malignancy, authors have evaluated change in 6-minute walk distance across a range of malignancies, including sarcomas, breast, colon, esophageal, and thyroid cancers (71). Additionally, the effect of treatment will hopefully be evident in differences in exercise tolerance, oxygen saturation, and dyspnea.
- Tumor/Disease Assessment: Chest CT scan to be performed *within 2 weeks* ± *l week treatment*. These CT scans will be used for the pre-treatment planning.
- Concomitant Medications: List any current medications taken within 1 week of study treatment.

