8.1.8 Initial Follow-Up Evaluation

The following evaluations will be performed **4 weeks** (± **1 week**) after the last study I-PDT and/or PDT (*unless otherwise indicated**):

- Physical examination (including vital signs)
- Hematology: Complete blood count (CBC) with automated differentials.
- Chemistry: Complete metabolic panel (CMP).
- Blood draw for immune markers
- ECOG Performance Status (Appendix A)
- Tumor/Disease Assessment: Chest CT scan
- Concomitant medications
- Quality of Life Questionnaire (Cohorts A and B; Appendix D)
- Adverse events (will be followed for 30 days following treatment/procedure)
- Schedule date/time for follow-up bronchoscopy with EBUS (without TBNA). TBNA will be performed only if clinically indicated outside the scope of this study. If a tumor is visible, tumor tissue biopsies (about 50-300 mg per biopsy, if feasible) will be collected for immune markers. NOTE: The bronchoscopy will not be performed at this visit.
- If EBUS is performed and a tumor is visible, tumor tissue biopsies (about 50-300 mg per biopsy, if feasible) will be collected for immune markers.

*Bronchoscopic and ultrasound images that are routinely obtained during therapeutic procedures will be used to evaluate the airway initially and during follow up. *Note: Initial follow-up bronchoscopy will be performed within 4 weeks following the first follow-up visit. Additional bronchoscopies will be performed as clinically indicated.*

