12.1.6 Phase II Sample Size Justification (Cohort A and Cohort B)

Let π equal the proportion of CR+PR responses. The primary analysis, for Cohort A and Cohort B, will consist of a one-sided exact binomial test of H₀: π =0.05 versus H_a: π >0.05 at level α =0.05. Given n=18 subjects and setting power at 0.80 we will be able to detect an alternative response rate of π >0.29. The primary analysis for Cohort B will consist of a one-sided exact binomial test of H0: π =0.30 versus Ha: π >0.30 at level α =0.05. Given n=39 subjects (including n=6 from the Phase I) and setting power at 0.80 we will be able to detect an alternative response rate of $\pi > 0.50$. A secondary analysis of efficacy will utilize an ordinal regression of response (CR, PR, SD, PD) as a function of baseline tumor volume. All key secondary outcomes will be considered suitably continuous will be analyzed with an analysis-of-covariance (ANCOVA) approach regressing change from baseline to three months on the baseline value of the respective measure adjusted for baseline tumor volume, age, and sex. The null hypothesis of interest is H₀: $\beta_0=0,\beta_1=0$ versus H_a: $\beta_0 \neq 0, \beta_1 \neq 0$, where β_0 is the ANCOVA intercept and β_1 is the regression slope, respectively. All tests will be at level α =0.05. Since both the FACT-L based measures and the 6-minute walk measures are likely to be highly cross correlated no adjustments for multiple testing will be considered a priori. For Cohort A and Cohort B, each continuous endpoint and given n=18 subjects we will have 0.80 power to reject the joint null hypothesis if the slope and intercept account for 39% of the overall variation or larger in the given endpoint. For Cohort B, each continuous endpoint and given n=39 subjects we will have 0.80 power to reject the joint null hypothesis if the slope and intercept account for 20% of the overall variation or larger in the given endpoint.

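### The three-month FACT-L and walk ANCOVAs have no rule for patients who die or are untested by week 12, so loss after deterioration would bias the mean change upward

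*Combined protocol and SAP*

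**What the plan says.** Section 3.1.2 makes change in well-being a primary Phase II objective. Section 4.1.2 lists "The FACT-L Total Score related subscale" and the walk measures as primary Phase II endpoints. Section 12.1.3 gives the primary role to CR+PR and treats these measures as additional efficacy endpoints, analysed by an "analysis-of-covariance (ANCOVA) approach regressing change from baseline to three months on the baseline value of the respective measure", adjusted for baseline tumour volume, age and sex.

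Section 12.1.6 states the null hypothesis jointly (intercept and slope both zero), sets the level at 0.05 without multiplicity adjustment, and computes power at full enrolment: for Cohort A, "each continuous endpoint and given n=18 subjects we will have 0.80 power to reject the joint null hypothesis" when the two terms explain 39% of the variation. The Cohort B figure is 20% at n=39.

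On data collection:
- Section 8.1.8 includes "Quality of Life Questionnaire (Cohorts A and B; Appendix D") at week 4. Section 8.1.9 repeats FACT-L at weeks 12 and 24 and schedules the walk test at weeks 12 and 24 only.
- Footnote 3 of Table 1 makes the long-term visits conditional on clinical indication.
- Section 8.1.10 follows survival status to 24 weeks for everyone, including after progression.
- Section 4.1.4 replaces only patients who never receive I-PDT or PDT.

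No section says how death or a missing week-12 test enters these ANCOVAs. There is no imputation, composite or worst-rank rule, efficacy analysis set, sensitivity analysis or dropout allowance.

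**The concern.** Change to three months can be computed only for patients who are alive and tested. Section 2 describes frail, terminal-stage patients, and Section 5.1 admits ECOG up to 3, so losses by week 12 are to be expected. If those lost are the ones who got worse after treatment, the patients left look better than the treated group did. With no concurrent control to share the distortion, it passes straight into the estimated mean change.

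Section 12.1.4 says the data will inform a randomised Phase IIb trial, so an inflated well-being estimate could carry into that design. The week-4 FACT-L score, which is informative about patients lost later, has no place in the three-month analysis.

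**Working it through.** **1. The plan's own power figures.** Inputs are from Section 12.1.6. With f² = R²/(1−R²), noncentrality λ = n·f², and an F test on 2 and n−3 df at 0.05:
- Cohort A: f² = 0.39/0.61 = 0.639; λ = 18 × 0.639 = 11.5; power 0.788. The stated 0.80 reproduces to rounding.
- Cohort B: f² = 0.20/0.80 = 0.25; λ = 39 × 0.25 = 9.75; power 0.769. For 0.80, R² must be about 0.21.

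Both use every enrolled patient. With an assumed 30% unavailable at week 12, Cohort A has 13 patients (λ = 8.3, power 0.59) and Cohort B has 27 (λ = 6.75, power 0.58).

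**2. Bias in the mean change, closed form.** Assume zero true mean change, a fraction q lost, and correlation r between a patient's latent change and the index that governs loss. Then

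bias = r × φ(z_q)/(1−q), in SDs of change.

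At q = 0.30, z = −0.524, φ(z) = 0.348 and 0.348/0.70 = 0.497. With r = 0.5 the bias is 0.5 × 0.497 = +0.25 SD. With r = 0.3 or 0.7 it is +0.15 or +0.35. At q = 0.20 and 0.40 with r = 0.5 it is +0.175 and +0.32. Both q and r are assumptions; the documents give neither.

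**3. Does baseline adjustment remove it?** Simulated baseline and latent week-12 scores, zero true mean change, correlation 0.5 or 0.7, and a loss index with equal-variance noise added. Entries are mean change in baseline SDs at 30% loss (correlation 0.5 / 0.7):

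| Loss tied to | Raw survivor mean | ANCOVA-adjusted |
|---|---|---|
| Nothing | 0.00 / 0.00 | 0.00 / 0.00 |
| Baseline severity | −0.17 / −0.11 | 0.00 / 0.00 |
| Latent week-12 state | +0.18 / +0.10 | +0.28 / +0.20 |
| The change itself | +0.35 / +0.27 | +0.28 / +0.24 |

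So adjustment removes the bias when loss depends on baseline alone, but not when loss follows later decline. Across 10% to 50% loss, the adjusted bias runs from +0.08 to +0.46 in the last two rows.

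**4. A test of the adjusted mean change.** With centred baseline, three further covariates, baseline to week-12 correlation 0.6 and 30% loss, the adjusted bias is about +0.25 SD when loss is tied to the week-12 state. A significant improvement is then declared in 33% of Cohort B trials and 13% of Cohort A trials, against a nominal 2.5%. With loss tied to the change, the rates are 39% and 15%.

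**5. If the true mean change is a decline of 0.5 SD.** At 30% loss tied to week-12 state or change, the adjusted survivor estimate is −0.22 to −0.30. The decline is understated rather than reversed.

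**6. What a mixed model recovers.** Take step 2 with q = 0.30 and r = 0.5, and let c be the correlation between week-4 and week-12 change. After selection, the variance of the loss index is 1 + (−0.524)(0.497) − 0.497² = 0.493. The slope of week-12 on week-4 change in the observed is c(1 − 0.25 × 0.507)/(1 − 0.25c² × 0.507), which is 0.652 at c = 0.7 and 0.451 at c = 0.5. Residual bias:
- c = 0.7: 0.248 − 0.652 × 0.5 × 0.7 × 0.497 = +0.135 SD
- c = 0.5: 0.248 − 0.451 × 0.5 × 0.5 × 0.497 = +0.19 SD

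More than half of the +0.25 SD remains.

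**The case against.** Several points on the other side stand.

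- **The plan does not say survivors only.** That is the default result of the stated method, inferred from the absence of any other rule.
- **A reader might infer that losing the sickest patients must produce an improvement.** The documents do not support that. The outcome is within-patient change with baseline in the model. If those lost were simply worst at baseline, the adjusted bias is zero and the raw survivor mean moves down. The upward bias needs loss linked to decline after treatment, which is plausible in progressive airway obstruction but assumed.
- **A reader might also take the 13% to 39% rates as error rates of the planned test.** They are not. Section 12.1.6 specifies a joint, non-directional test of intercept and slope. With baseline centred, zero mean change and no losses, that test rejected in 24% to 40% of simulations at n=18 and 57% to 82% at n=39 (correlation 0.7 to 0.5), through regression to the mean alone. Its rejection is therefore not evidence of improvement. The joint test also does nothing to protect the mean change that readers will interpret.
- **Mortality by week 12 is unknown.** Section 1.1.10 reports "3 out of 10 patients alive at 8.3, 12, and 26.5 months", which does not say how many had died by three months.
- **Direction could differ.** If visits occur only on clinical indication, as Table 1 footnote 3 has it, symptomatic patients could be over-represented, which would pull the estimate down.
- **The stakes are bounded.** The CR+PR binomial tests do not use these ANCOVAs, death is a PFS event, and survival status is collected, so deaths will be visible. Neither PFS nor survival status is linked to the FACT-L or walk result.

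**Conclusion.** The gap is real and should be closed. The three-month FACT-L and walk ANCOVAs have no rule for death or missing tests, and the method as stated drops those patients in an uncontrolled, palliative population. Where loss follows post-treatment deterioration, the estimated mean change is too favourable by about +0.25 SD at 30% loss. This rests on an assumed loss fraction, an assumed link between loss and decline, and zero true change. The same selection would shrink a true decline. Nothing in the documents fixes the actual size or guarantees the direction, and there is no adjusted bias if loss depends on baseline alone. Apart from bias, power at the stated effect sizes falls from about 0.77 to 0.79 at full enrolment to just under 0.60 at 30% loss. Enrolling more patients would restore power but leave the bias.

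**What to change.** - **Composite result, beside the ANCOVA and with equal prominence.** For FACT-L and for walk distance, report the proportion of all treated patients who are alive and improved at week 12 by a pre-specified threshold. Count death, too ill to be tested, or missing as not improved. The thresholds must be written in: Section 8.1.2 says of FACT-L that "prior research has quantified the minimal clinically important difference" but gives no value, and no threshold for walk distance appears anywhere.
- **Losses.** Report the numbers lost before week 12 by reason (death, too ill, other missing) next to each FACT-L and walk result. State power at the expected evaluable number as well as at 18 and 39.
- **Secondary step for FACT-L.** Fit a mixed model to the week 4, 12 and 24 scores already collected, with the same covariates, and state that it reduces but does not remove bias from death. The walk test has no week-4 measurement, so this step does not extend to it in the same form.

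The data needed (FACT-L, walk test, survival status to 24 weeks) are already in the schedule. The cost is plan wording and modest analysis work, and the well-being result will probably look less favourable.
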